1. Study Title

Association of the $\text{PaO}_2/\text{PaCO}_2$ Ratio With ICU Mortality Independent of Oxygen Saturation and Mean Arterial Pressure: A MIMIC-II Retrospective Cohort Study

Acronym: RATIO-MIMIC

2. Study Objectives

Primary Objective:

- To determine whether the $\text{PaO}_2/\text{PaCO}_2$ ratio is independently associated with ICU mortality in critically ill adults, adjusting for oxygen saturation (SpO_2) and mean arterial pressure (MAP).

Secondary Objectives:

- To explore the relationship between $\text{PaO}_2/\text{PaCO}_2$ ratio categories (e.g., tertiles or quartiles) and ICU length of stay.
- To perform subgroup analyses by mechanical ventilation status, age, or primary ICU diagnosis.

3. Study Design

- **Type:** Observational
- **Design:** Retrospective cohort study
- **Population:** Adult ICU patients (≥ 18 years) in MIMIC-II database
- **Sampling Method:** Retrospective census of all eligible patients meeting inclusion/exclusion criteria
- **Cohorts/Groups:** Single cohort; exposure analyzed as continuous and categorical (quartiles or tertiles)
- **Time Frame:** ICU admissions from 2001–2008 (MIMIC-II database)

4. Study Population

Inclusion Criteria:

1. Adult patients (≥ 18 years) at ICU admission
2. First (index) ICU admission during hospitalization

3. At least one arterial blood gas measurement with PaO_2 and PaCO_2
4. Available SpO_2 and MAP during ICU stay
5. Documented ICU discharge status

- **Exclusion Criteria:**
 1. Age <18 years
 2. Missing or non-numeric PaO_2 or PaCO_2 values
 3. Missing ICU outcome data
 4. Physiologically implausible ABG values
 5. ECMO during ABG measurement (if identifiable)
 6. No SpO_2 or MAP measurements during ICU stay
 7. Repeat ICU admissions beyond index stay
 8. DNR/comfort-care orders prior to ABG measurement (optional for sensitivity analyses)

5. Data Collection and Variables

- **Exposure Variable:** $\text{PaO}_2/\text{PaCO}_2$ ratio (calculated from ABG measurements)
- **Outcome Variable:** ICU mortality (yes/no)
- **Covariates for Adjustment:**
 - Oxygen saturation (SpO_2)
 - Mean arterial pressure (MAP)
 - Age, sex, ICU type (medical/surgical), comorbidities (if available)
 - Mechanical ventilation status
- **Time Points:** First ABG per ICU stay (primary), or median/peak ABG values for sensitivity analysis

6. Statistical Analysis Plan (SAP)

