6.2 Primary Analysis

- **Model:** Multivariable logistic regression
- **Dependent Variable:** ICU mortality (binary)
- **Independent Variable:** $\text{PaO}_2/\text{PaCO}_2$ ratio (continuous or categorical)
- **Covariates:** SpO_2 , MAP, age, sex, ICU type, comorbidities
- **Effect Measures:** Adjusted odds ratios (ORs) with 95% confidence intervals
- **Assessment of Independence:** Evaluate whether $\text{PaO}_2/\text{PaCO}_2$ remains statistically significant after adjustment

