6.3 Secondary Analyses

- **Subgroup Analyses:** Mechanical ventilation status, age categories, ICU type
- **Sensitivity Analyses:**
 - Excluding extreme ABG values
 - Excluding DNR/comfort-care patients
 - Using alternative $\text{PaO}_2/\text{PaCO}_2$ calculation methods (first ABG vs. median ABG)
- **Time-to-event Analysis (Optional):** Cox proportional hazards for ICU length of stay, treating death as event

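### The primary model contains no measure of the reason for ICU admission, so residual confounding may pass the plan's significance-only test of independence

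*Combined protocol and SAP*

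**What the plan says.** - **Cohort (section 3):** "Retrospective census of all eligible patients meeting inclusion/exclusion criteria". The criteria in section 4 restrict by age, index stay and data availability, and exclude ECMO and, optionally, comfort care. They do not restrict by diagnosis.
- **Primary model (section 6.2):** "Multivariable logistic regression" for ICU mortality, with covariates "SpO_2 , MAP, age, sex, ICU type, comorbidities".
- **Definition of those covariates (section 5):** "ICU type (medical/surgical), comorbidities (if available"). ICU type is shown with two levels, and comorbidities are conditional on availability. Section 5 also lists mechanical ventilation status for adjustment, which section 6.2 does not.
- **Diagnosis (section 2, secondary objectives):** "To perform subgroup analyses by mechanical ventilation status, age, or primary ICU diagnosis". This is its only appearance.
- **Subgroups in the SAP (section 6.3):** "Mechanical ventilation status, age categories, ICU type".
- **Test of independence (section 6.2):** whether the ratio "remains statistically significant after adjustment", at a two-sided 0.05 level (section 6.5).

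**The concern.** The primary objective is an association that holds independently of other factors, and section 6.2 settles it by significance after adjustment. The covariate list therefore decides the main conclusion.

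In a mixed ICU population, patients admitted for different reasons may arrive on different oxygen and ventilatory support, and so with different first-gas ratios. They may also differ in risk of death. A two-level unit term removes the average difference between medical and surgical patients but leaves variation within each type. An elective post-operative patient and an emergency surgical patient share one value, as may a cardiac and a septic medical patient. Comorbidities describe chronic conditions rather than the reason for this admission, and may be absent.

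None of the sensitivity analyses in section 6.3 changes the adjustment set. They vary the blood-gas values used or exclude patients, so they are not designed to reveal this bias.

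**Working it through.** **No figure to reproduce.** The documents give no sample size, event count, mortality rate or effect size. The check compares the lists, then illustrates.

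**Step 1: where each variable appears.**

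| Variable | Section 2 | Section 5 covariates | 6.2 model | 6.3 subgroups |
|---|---|---|---|---|
| Primary ICU diagnosis | optional subgroup | no | no | no |
| ICU type | no | yes, two levels | yes | yes |
| Comorbidities | no | if available | yes | no |
| Mechanical ventilation | optional subgroup | yes | no | yes |

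No other admission-reason variable, and no severity score, is listed anywhere.

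**Step 2: condition for bias.** With no true ratio effect, leaving out admission group G biases the ratio's odds ratio only if, given the other covariates, G relates to both the ratio and death. The sign of the bias in the log odds ratio is the sign of (shift in ratio with G) × (log odds ratio of death with G).

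**Step 3: illustration A (all inputs assumed).** Half the cohort is surgical. Of these, 30, 50 or 60% are routine post-operative, with a ratio 0.5 or 0.8 SD higher and mortality 2 or 3%, against 12% elsewhere. The true odds ratio for the ratio is 1. The implied odds ratio for death in the routine group is (0.02/0.98)/(0.12/0.88) = 0.15, or (0.03/0.97)/(0.12/0.88) = 0.23, which is a strong contrast. The fitted model is logit P(death) = a + b × ratio (per SD) + c × ICU type, without SpO2, MAP, age or comorbidities. I solved the expected likelihood equations by numerical integration, so these figures carry no simulation error; expected z is b/SE(b), scaled by √n.

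| Routine share | Shift (SD) | Mortality | OR per SD | Expected z, n = 5,000 |
|---|---|---|---|---|
| 30% | 0.5 | 2% / 3% | 0.946 / 0.952 | -1.20 / -1.07 |
| 30% | 0.8 | 2% / 3% | 0.916 / 0.925 | -1.88 / -1.68 |
| 50% | 0.5 | 2% / 3% | 0.929 / 0.938 | -1.49 / -1.33 |
| 50% | 0.8 | 2% / 3% | 0.890 / 0.903 | -2.35 / -2.09 |
| 60% | 0.5 | 2% / 3% | 0.928 / 0.937 | -1.48 / -1.31 |
| 60% | 0.8 | 2% / 3% | 0.887 / 0.901 | -2.32 / -2.05 |

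The range is 0.89 to 0.95. With the admission group added, the true value is 1, and simulation of 400,000 patients per setting returned 0.99 to 1.01.

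Expected |z| exceeds 1.96 in 4 of 12 settings at n = 5,000, 8 at n = 10,000 (z × √2) and 12 at n = 20,000 (z × 2). Simulation gave 5, 10 and 12. Its error on z at n = 5,000 is about √(5,000/400,000) = 0.11, enough to move settings near the threshold. The n at which |z| reaches 1.96 is 5,000 × (1.96/2.35)² ≈ 3,500 in the strongest setting and 5,000 × (1.96/1.07)² ≈ 17,000 in the weakest.

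**Step 4: illustration B (different assumed inputs).** A diagnosis is present in 20% of one unit type and 40% of the other. Baseline mortality is 10%, the diagnosis odds ratio for death is 1 to 3, and the ratio shifts by -0.8 to +0.5 SD. The model adjusts for ICU type and one comorbidity. Without the diagnosis, a true null gave odds ratios from 0.83 (odds ratio 3, shift -0.8) to 1.13 (odds ratio 3, shift +0.5), and 1.00 when the diagnosis did not affect mortality. With it, they were 1.000 to 1.004. Making the comorbidity correlate with diagnosis removed little of the bias (0.89 became 0.90).

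**The case against.** The strongest reply is that the model is not bare. Age, sex, MAP and, if available, comorbidities all carry some case mix, and SpO2 is physiologically tied to PaO2, so conditioning on it could change the result materially. Illustration A includes none of these and so does not test the planned model. This stands: the odds ratios show that the mechanism can work, not how large it would be here. It also means that a reader who inferred that ICU type is the only case-mix control would be wrong.

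A reader might also infer that differences between units are attributed to the ratio. Differences between the two ICU types are adjusted for; only variation within a type is at issue.

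Nor does the plan commit to extracting diagnosis. It is one of three options joined by an *or*, section 6.3 does not carry it over, and section 5 lists no such variable. The documents do not show that diagnosis, elective status or finer unit codes are recorded in usable form.

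Finally, significance is not assured. At n = 5,000, 8 of the 12 settings in illustration A stay below the threshold on expectation.

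What this does not answer is that no listed covariate measures the reason for admission, and that a significance-only criterion becomes easier to pass by confounding as the cohort grows. Adding mechanical ventilation, as section 5 has it, could absorb part of the effect but would not replace admission reason.

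**Conclusion.** The point holds as a risk of residual confounding by admission reason that the plan neither controls nor examines. It rests on the covariate lists, the diagnostically unrestricted census and the section 6.2 criterion, all of which are in the text. The discrepancy between the subgroup lists in section 2 and section 6.3 is likewise plain from the text.

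Size and direction are not established. The figure of 0.89 to 0.95 depends on assumed shares, shifts and mortality, and on a reduced model; illustration B reaches 0.83 to 1.13 under other assumptions. A reader might infer that a high ratio will appear protective. That follows only if patients with high ratios are those admitted for low-risk reasons, and the documents give no data on this. The supported conclusion is that a significant adjusted odds ratio from the listed model would not by itself show independence from the reason for admission.

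**What to change.** 1. In sections 5 and 6.2, add a prespecified primary ICU diagnosis (admission-reason) category as a covariate in the primary model, separating elective from emergency post-operative admissions where recorded. Fix the categories, and a rule for merging sparse ones, before outcomes are examined.
2. Use the finest care-unit type recorded, where available, in place of the two-level ICU type. The two-level version can remain as a subgroup label.
3. Align the subgroup lists in sections 2 and 6.3, so that primary diagnosis is either analysed or removed. Reconcile at the same time the presence of mechanical ventilation in the section 5 covariates with its absence from section 6.2.
4. If admission reason proves unavailable, say so and state the resulting limit on any claim of independence.

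The cost is extracting and grouping a variable that section 5 does not yet list, covering it in the missing-data rule of section 6.4, and a few degrees of freedom. How much those matter depends on the number of deaths, which the documents do not give.

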6.1 Descriptive Analysis

- Continuous variables: mean \pm SD or median (IQR)

- Categorical variables: counts and percentages
- Compare baseline characteristics across $\text{PaO}_2/\text{PaCO}_2$ quartiles using ANOVA/Kruskal-Wallis for continuous variables and chi-square/Fisher's exact test for categorical variables

6.2 Primary Analysis

- **Model:** Multivariable logistic regression
- **Dependent Variable:** ICU mortality (binary)
- **Independent Variable:** $\text{PaO}_2/\text{PaCO}_2$ ratio (continuous or categorical)
- **Covariates:** SpO_2 , MAP, age, sex, ICU type, comorbidities
- **Effect Measures:** Adjusted odds ratios (ORs) with 95% confidence intervals
- **Assessment of Independence:** Evaluate whether $\text{PaO}_2/\text{PaCO}_2$ remains statistically significant after adjustment

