6.5 Statistical Software

- R (version ≥ 4.0) or STATA (version ≥ 16)
- Two-sided p-value <0.05 considered statistically significant

7. Ethical Considerations

- Secondary analysis of **de-identified public data (MIMIC-II)**
- No new patient consent required
- Approved by MIT and Beth Israel Deaconess Medical Center Institutional Review Boards for public data use

8. Reporting

- Follow **STROBE guidelines** for observational studies
- Present baseline tables, regression results, and flowchart of included/excluded patients
- Include sensitivity and subgroup analyses
- Report odds ratios, 95% CI, and p-values

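### The primary model holds the PaO2/PaCO2 ratio but neither gas separately, so a significant ratio cannot be told apart from an effect of one gas alone

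*Combined protocol and SAP*

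**What the plan says.** Section 2 asks whether the ratio is independently associated with ICU mortality, "adjusting for oxygen saturation (SpO_2) and mean arterial pressure (MAP"). The title limits independence in the same way. Section 5 describes the exposure only as "calculated from ABG measurements".

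Section 6.2 specifies "Multivariable logistic regression" for ICU mortality. The exposure is the PaO2/PaCO2 "ratio (continuous or categorical", and the covariates are "SpO_2 , MAP, age, sex, ICU type, comorbidities". The test of independence is whether the ratio "remains statistically significant after adjustment", at the level set in 6.5: "Two-sided p-value <0.05 considered statistically significant".

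The covariate list in Section 5 adds mechanical ventilation, but neither gas. The sensitivity analyses in 6.3 drop extreme blood gas values, drop DNR/comfort-care patients, or change which blood gas is used. None enters PaO2 and PaCO2 separately. Inclusion criterion 3 requires "At least one arterial blood gas measurement with PaO_2 and PaCO_2", so both values exist for every patient analysed.

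**The concern.** A ratio entered alone carries a hidden constraint. Whether it is used raw, logged or in quartiles, it depends on the gases only through log PaO2 minus log PaCO2. On the log scale this forces the two gases to have equal and opposite effects, and the plan never examines whether they do. A PaO2 of 60 with a PaCO2 of 40 and a PaO2 of 120 with a PaCO2 of 80 both give 1.5 and contribute identically through the exposure term.

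A ratio is also correlated by construction with its numerator and its denominator. If only one gas is related to mortality, the ratio picks up part of that relation and may meet the plan's criterion. Neither SpO2 nor MAP measures PaCO2, so adjusting for them does not remove a PaCO2 effect.

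The ratio is the named exposure in the title and the acronym. A positive result will be read as evidence about the ratio, and the plan has no analysis that could show whether one gas alone produced it.

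**Working it through.** The documents state no sample size, event rate or effect size, so there is no figure of the plan's to reproduce. The check is algebra followed by simulation on assumed inputs.

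**1. The constraint.** With the log ratio as exposure, the linear predictor contains β·log(PaO2/PaCO2) = β·log PaO2 − β·log PaCO2. This is the model with separate terms βO·log PaO2 + βC·log PaCO2, restricted to βO = −βC. It is nested, with one degree of freedom. The log ratio cannot be entered together with both log gases, because the three are linearly dependent (design rank 3 of 4, counting the intercept). The raw ratio and quartiles in 6.2 are not nested in the linear log model, so a nested test first requires the log ratio to be fitted.

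**2. How closely the ratio follows each gas.** Assume log-SDs of 0.5 (PaO2) and 0.25 (PaCO2) and a log-correlation of −0.1.

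- Variance of the log ratio: 0.25 + 0.0625 + 2(0.1)(0.5)(0.25) = 0.3375; SD 0.581.
- Correlation with log PaO2: (0.25 + 0.0125)/(0.5 × 0.581) = 0.90.
- Correlation with log PaCO2: −(0.0625 + 0.0125)/(0.25 × 0.581) = −0.52.

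Under these assumptions the log ratio is close to a stand-in for log PaO2 and moderately related to log PaCO2.

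**3. How often a one-gas effect makes the ratio significant.** Further assumptions: 12% mortality; median PaO2 120 and PaCO2 40; SpO2 from a saturation curve plus noise, capped at 100; SpO2, MAP and age as covariates. Mortality depends on one log gas plus those covariates, with no separate ratio effect. The test is a two-sided Wald test at 0.05 on the continuous ratio, with 400 runs per cell (200 at N = 10,000).

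| True effect (OR per SD of log gas) | N = 1,000 | N = 3,000 | N = 10,000 |
|---|---|---|---|
| Neither gas | 4% | 6% | 4% |
| PaCO2 only, 1.15 | 10% | 22% | 57% |
| PaCO2 only, 1.30 | 26% | 65% | 99% |
| PaO2 only, 1.15 | 10% | 29% | 77% |
| PaO2 only, 1.30 | 29% | 75% | 99.5% |

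The test is sound when neither gas matters, so the excess comes from the single-gas effect. Quartiles (3-df test) gave 7% to 99% over the same one-gas scenarios and do not solve the problem. Adding both log gases to the raw-ratio model brought the ratio term back to 3-8%.

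Runs with about 10% mortality and odds ratios of 1.15 to 1.28 gave roughly 10-20% at N = 1,000, 27-86% at 5,000 and 69-100% at 15,000.

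**4. What SpO2 adjustment covers.** When risk ran entirely through measured SpO2, the planned ratio was significant in 4-5% of runs at N = 1,000, 5,000 and 15,000, which is nominal. The PaO2 rows above arise because PaO2 was assumed to matter beyond measured SpO2.

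**5. Whether the 1-df test alone would settle it.** In PaO2-only scenarios:

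| OR, N | Constraint rejected | Log ratio significant and constraint not rejected |
|---|---|---|
| 1.28, 1,000 | 14% | 21% |
| 1.28, 5,000 | 51% | 36% |
| 1.15, 15,000 | 46% | 39% |

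Across such scenarios the last column reached 45%. For a PaCO2-only effect (OR 1.28) at N = 5,000 and 15,000, by contrast, the test rejected in 99-100% of runs. The asymmetry follows from step 2.

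**The case against.** The strongest reply is that the plan answers the question it asks. Title and objective define independence relative to SpO2 and MAP, and the language is of association. Nothing says the ratio outperforms or adds to either gas. This stands: a reader might infer that a significant ratio would be a false positive, but the documents do not support that. It would be a valid association adjusted for SpO2 and MAP. The reply does not remove the difficulty that the plan offers no means of saying what lies behind the association.

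Three other stronger readings also go too far.

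- That a one-gas effect *will* be declared a ratio effect. The probability ran from about 10% to nearly 100% over the assumed inputs, and the documents fix neither cohort size nor effect size.
- That the plan has no protection against confusing the ratio with hypoxaemia. SpO2 is a covariate and absorbs risk that runs through measured saturation. For the same reason, the two patients who share a ratio of 1.5 would generally differ in SpO2, so the model need not give them the same overall risk.
- That non-rejection of the equal-and-opposite constraint would establish a ratio effect. Step 5 shows it would often endorse a pure PaO2 effect. The result also depends heavily on cohort size: with both gases contributing in opposite directions but unequally (−0.4 and +0.8 per log unit), the test rejected in 79% of runs at N = 15,000.

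**Conclusion.** The point holds as a limit on what the primary analysis can show. The ratio is the only blood-gas term in every planned model, and its significance after adjustment is the only criterion of independence. An effect of PaCO2 alone, or of PaO2 beyond SpO2, can meet that criterion, and the chance rises with cohort size and effect size. Section 3 plans a census of eligible admissions from 2001 to 2008, and a larger cohort makes this more likely, not less.

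The percentages are illustrative. They rest on assumed mortality, gas distributions, saturation curve and effect sizes, none of which the documents give. The absence of a component model and the algebraic constraint do not depend on those assumptions. The analysis can run as written, but a conclusion about the ratio itself would lack support, so the change should be made.

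**What to change.** In 6.2, pre-specify a companion logistic model with the same covariates and with log PaO2 and log PaCO2 as separate terms in place of the ratio. Report both coefficients with 95% CIs whatever the result. Do not standardise the two log gases separately, because the equal-and-opposite constraint applies to coefficients per log unit.

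Also fit the log ratio with the same covariates. Give the 1-df likelihood-ratio test of equal and opposite coefficients as supporting information only, not as a gate.

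State in advance that a conclusion will be attributed to the ratio itself only if the component coefficients have opposite signs, each CI excludes zero, and the CIs are compatible with equal magnitude. If only one gas matters and the model is otherwise right, the other gas's CI excludes zero in the required direction about 2.5% of the time (5%/2), so a one-gas effect would seldom pass. Otherwise, report the component effects and limit the ratio conclusion to association adjusted for SpO2 and MAP.

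The cost is one or two extra models, no new data (inclusion criterion 3 already requires both gases), and possibly a narrower conclusion.

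### The primary model has no measure of acid-base state, so a significant PaO2/PaCO2 ratio could not be read as independent of metabolic acidosis

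*Combined protocol and SAP*

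**What the plan says.** The primary objective asks whether the ratio "is independently associated with ICU mortality in critically ill adults, adjusting for oxygen saturation" and mean arterial pressure. Section 5 derives the exposure from arterial blood gases and sets its timing as "First ABG per ICU stay (primary), or median/peak ABG values for sensitivity analysis".

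The covariates of the primary logistic model in section 6.2 are "SpO_2 , MAP, age, sex, ICU type, comorbidities". The list in section 5 differs in two ways: it adds mechanical ventilation status, and it includes comorbidities only if available. Neither list, and none of the subgroup or sensitivity analyses in section 6.3, names pH, bicarbonate, base excess, lactate or an acute severity score.

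Independence is assessed in section 6.2 by whether the ratio "remains statistically significant after adjustment". Section 6.5 sets the threshold: "Two-sided p-value <0.05 considered statistically significant". No direction of effect is specified, so a significant OR on either side of 1 would meet the criterion.

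**The concern.** The ratio rises when PaO2 rises or when PaCO2 falls. One reason for a low PaCO2 in critical illness is respiratory compensation for metabolic acidosis. This is general physiology and is not stated in the documents; the dependence of the ratio on PaCO2 is arithmetic. A high ratio can therefore mark good oxygenation or compensated acidosis, and these plausibly carry opposite prognoses.

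A factor that lowers PaCO2 and raises mortality confounds the ratio OR unless the model accounts for it. SpO2 and MAP can be normal in a compensated patient, and age, sex, ICU type and comorbidities do not measure acute acid-base state. If a low ratio is itself harmful, the same mechanism could mask that effect. What is at stake is how far the word *independent* can be taken when the result is reported.

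**Working it through.** The documents give no sample size, event count or expected effect, so there is no planned figure to reproduce. The check has five steps. All numerical inputs are assumptions.

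**1. Arithmetic of the exposure.** Ratio = PaO2 / PaCO2. At PaO2 90 mmHg: 90/40 = 2.25 and 90/28 = 3.21. The relative change is 3.21/2.25 = 1.43, a rise of 43% with PaO2 unchanged.

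**2. Simulation without other covariates.** Each scenario had 400,000 patients and no effect of the ratio on death.
- PaO2: lognormal, median 110 mmHg, log-SD 0.45, unrelated to acidosis.
- PaCO2: lognormal, log-SD 0.15, median 40 mmHg, or 25 to 32 mmHg if acidotic.
- Acidosis in 10 to 25% of patients; mortality 30% with it and 10% without.

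With acidosis omitted, the OR per SD of log ratio was 1.09 to 1.31, and the OR for top versus bottom quartile 1.23 to 1.96. The central case (15% acidotic, median PaCO2 28 mmHg) gave 1.18 per SD and 1.50 between those quartiles.

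**3. Dependence on PaO2.** In the central case the median ratio without acidosis is 110/40 = 2.75. Lowering the median PaO2 of acidotic patients changes the result:

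| Median PaO2 if acidotic (mmHg) | Median ratio if acidotic | OR per SD, no true effect |
|---|---|---|
| 110 | 110/28 = 3.93 | 1.18 |
| 90 | 90/28 = 3.21 | 1.08 |
| 77 | 77/28 = 2.75 | 1.00 |
| 70 | 70/28 = 2.50 | 0.95 |

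The bias vanishes where the two median ratios coincide and reverses below that. Adding a MAP term changed little: 1.17, 1.07 and 1.00 for the first three rows.

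**4. Simulation closer to the planned model.** The model held log ratio, SpO2, MAP and age, with 200 replicates per scenario. Baseline mortality was about 10%, acidosis prevalence 15 or 30%, acidosis-death OR 2 or 4, PaCO2 lower by 5 or 10 mmHg, and MAP lower by 0.5 SD in acidosis. Sex, ICU type, comorbidities and ventilation were not simulated.

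| N | Ratio significant, acidosis omitted | OR per SD |
|---|---|---|
| 2,000 | 4 to 77% | 1.03 to 1.23 |
| 10,000 | 14 to 100% | 1.03 to 1.23 |

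MAP removed only part of the bias. At N = 10,000, prevalence 20%, OR 3 and PaCO2 lower by 8 mmHg, the ratio was significant in 84% of replicates with no MAP shift and in 66% with a 1.5 SD shift. In the same setting with a 0.5 SD MAP shift, lowering log PaO2 in acidosis by 0.10, 0.22 and 0.40 gave 56%, 17% and 12%, with ORs of 1.08, 1.04 and 0.97.

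**5. What adjustment recovers.** With the true acidosis indicator in the model, the OR per SD was 0.99 to 1.00 in the step 2 scenarios and 0.99 to 1.01 in those of step 4, where the ratio was significant in 2 to 7% of replicates. That indicator is error-free and is the only omitted confounder, so this is a best case. Replacing it with a noisy base-excess term in the central case, with the MAP term, moved the OR from 1.17 to 1.08. This removed (1.17 − 1.08)/(1.17 − 1.00) = 0.09/0.17, about half the bias. The noise level is also an assumption.

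**The case against.** The strongest reply is that the objective defines independence relative to SpO2 and MAP, and claims an association rather than a mechanism. A ratio that predicts death because it marks acidosis would still meet that wording. This stands. A reader might infer that the primary objective goes unanswered, but the documents never say that the ratio isolates gas exchange, so they do not support that reading.

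A second reply is that some planned elements bear on the problem. MAP and comorbidities correlate with acidosis. Section 5 lists ventilation status, and PaCO2 under controlled ventilation is partly set by the ventilator, so compensation does not act uniformly. Section 2 foresees subgroups by primary ICU diagnosis, section 3 allows categorical exposure, and section 6.1 compares characteristics across quartiles. It would therefore be too strong to say that nothing planned captures acidosis at all. These are partial proxies and checks, however, and none adjusts the primary OR for acid-base state. Excluding extreme gases, excluding DNR or comfort-care patients, or using the median gas (section 6.3) does not do so either.

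A third reply is that size and sign depend on the chosen inputs, notably PaO2 being unrelated to acidosis. This also stands, as step 3 shows. A reader might infer that a falsely positive OR is to be expected; the documents give no basis for predicting that.

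**Conclusion.** The point holds as a limit on interpretation and a worthwhile improvement to the plan. The 6.2 model has no acid-base measure, and its criterion for independence cannot separate an effect of the ratio from confounding by compensated metabolic acidosis. With no true effect and assumed inputs, the OR per SD ranges from about 1.0 to 1.3. The upper end comes from the simulation without covariates; with SpO2, MAP and age in the model the highest value was 1.23. The OR falls below 1 (0.95 and 0.97 in the cases tried) if acidotic patients also have markedly lower PaO2. With small shifts and N = 2,000 the false-positive rate can stay near 5%.

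The conclusion rests on two premises from outside the documents: that compensated acidosis lowers PaCO2 in a relevant share of these patients, and that it raises mortality beyond what the planned covariates explain. A reader might also infer that adding base excess would settle the matter. It would not: the return to 1.00 needs a perfectly measured confounder.

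**What to change.** In section 6.2, prespecify a second model, identical to the primary one except that it adds base excess (or bicarbonate) from the index blood gas, where recorded, as a flexible term such as a spline. Base excess is preferable to pH, which PaCO2 itself alters. Report the ratio OR with and without the term, in the same patients, so that a change in the estimate is not a change of sample.

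Replace the independence criterion with a statement that limits the word to the variables actually adjusted for. Claim independence from metabolic acidosis only if the association persists in the second model. State that base excess is an imperfect measure, so residual confounding remains, and that chronic hypercapnia also raises bicarbonate, which is why both models are shown.

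The cost is one more variable, normally reported with the gas that supplies the exposure, and one more model. The documents do not say whether base excess is extracted or how complete it is. Some values will probably be missing, so it should be added to the covariates covered by section 6.4.

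### Inspired oxygen (FiO2) is absent from the exposure, covariates, subgroups and sensitivity analyses, so the primary odds ratio mixes gas exchange with oxygen treatment

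*Combined protocol and SAP*

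**What the plan says.** Section 5 defines the exposure as the PaO2/PaCO2 ratio, "calculated from ABG measurements", with the time point given as "First ABG per ICU stay (primary), or median/peak ABG values for sensitivity analysis". Nothing requires the sample to be on room air or to have a recorded FiO2.

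Section 6.2 specifies "Multivariable logistic regression" for ICU mortality with covariates "SpO_2 , MAP, age, sex, ICU type, comorbidities". Section 5 lists one more adjustment variable, ventilation status, which 6.2 does not carry forward. Elsewhere it is only a subgroup factor (Sections 2 and 6.3).

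Independence is judged in 6.2 by whether the ratio "remains statistically significant after adjustment", and 6.5 sets the threshold: "Two-sided p-value <0.05 considered statistically significant".

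FiO2, or any other measure of how much oxygen the patient was receiving, is not mentioned in eligibility, exposure, covariates, subgroups, sensitivity analyses or the missing-data rule. The nearest provisions are the exclusion of patients on ECMO at the time of the sample (where identifiable), the sensitivity analysis that drops extreme blood-gas values, and the ventilation subgroup. None of them measures FiO2.

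**The concern.** The numerator of the exposure depends directly on a treatment setting. For the same lungs, more inspired oxygen gives a higher PaO2 and a higher ratio. If clinicians give more oxygen to sicker patients, illness severity is a common cause of FiO2 and of death. Severe illness then lowers the ratio through worse gas exchange and raises it through more oxygen, and the two effects oppose each other in one coefficient.

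SpO2 is the covariate that might be expected to absorb this. It cannot do so well, because saturation is close to its ceiling over most of the range in which FiO2 moves PaO2.

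What is at stake is the meaning of the primary odds ratio. A weak or null result could hide a real gas-exchange association. A significant result in either direction could partly reflect how oxygen was given, and the 6.2 rule would still call it independent.

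**Working it through.** The plan states no sample size, event count or effect size, so there is no figure to reproduce. The checks below use assumed inputs, not values from the document.

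**1. How far FiO2 alone can move the ratio.** Alveolar gas equation with 760 mmHg, water vapour 47, PaCO2 40 and respiratory quotient 0.8: PAO2 = FiO2 × 713 − 40/0.8. Dividing by 40 gives the ceiling on the ratio; multiplying by an assumed arterial/alveolar (a/A) oxygen ratio gives the ratio itself.

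| FiO2 | PAO2 (mmHg) | Ceiling | Ratio, a/A 0.3 | Ratio, a/A 0.5 | Ratio, a/A 0.8 |
|---|---|---|---|---|---|
| 0.21 | 99.7 | 2.5 | 0.75 | 1.25 | 1.99 |
| 0.40 | 235.2 | 5.9 | 1.76 | 2.94 | 4.70 |
| 0.60 | 377.8 | 9.4 | 2.83 | 4.72 | 7.56 |
| 1.00 | 663.0 | 16.6 | 4.97 | 8.29 | 13.26 |

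The full range is 663.0/99.7, about 6.6-fold. Ranking can invert: poor lungs (a/A 0.3) on FiO2 1.00 give 4.97, and good lungs (a/A 0.8) on room air give 1.99.

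**2. Whether SpO2 absorbs it.** Saturation = 100/(1 + 23400/(P³ + 150P)), where P is PaO2. At a/A 0.5, going from FiO2 0.40 to 1.00 takes the ratio from 2.94 to 8.29 (2.8-fold) while saturation goes from 98.6% to 99.9%. In the inverted pair above, saturation is 99.7% for the poor lungs and 95.7% for the good lungs, so SpO2 ranks them the same wrong way.

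**3. Effect on the odds ratio.** Simulated cohorts of 60,000 with mortality about 10–11%. Main assumptions:
- Latent severity S (SD 1) lowers the a/A ratio and MAP, raises PaCO2 slightly, makes ventilation more likely, and raises the log-odds of death by 0.5 or 0.8 per SD.
- FiO2 = 0.45 + k·S + 0.10 if ventilated + noise (SD 0.15), limited to 0.21–1.00. Here k is the strength of titration to severity. At k = 0 a weak link remains through ventilation.
- FiO2 has no direct effect on death.

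Every model includes SpO2, MAP and age. Sex, ICU type and comorbidities were not simulated. Odds ratios are per SD of the ratio; paired entries are for severity log-odds 0.5 / 0.8.

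| k per SD | No FiO2 or ventilation | Ventilation added | Ventilation and FiO2 added |
|---|---|---|---|
| 0 | 0.79 / 0.69 | 0.79 / 0.69 | 0.70 / 0.58 |
| 0.05 | 0.88 / 0.80 | 0.86 / 0.79 | 0.78 / 0.66 |
| 0.10 | 0.93 / 0.86 | 0.92 / 0.84 | 0.83 / 0.70 |
| 0.15 | 0.98 / 0.93 | 0.96 / 0.90 | 0.85 / 0.75 |
| 0.20 | 1.04 / 1.00 | 1.02 / 0.96 | 0.90 / 0.81 |
| 0.25 | 1.06 / 1.08 | 1.04 / 1.04 | 0.90 / 0.85 |

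Without FiO2 or ventilation status, the twelve scenarios divide as follows:
- **Attenuated, interval still below 1:** seven.
- **Masked, interval including 1:** two, 0.98 (0.95–1.01) and 1.00 (0.97–1.03).
- **Reversed, interval above 1:** three, 1.04 (1.01–1.08), 1.06 (1.03–1.10) and 1.08 (1.05–1.11), all at k of 0.20 or 0.25.

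With ventilation status and FiO2 added, all twelve upper 95% limits lie below 1. Ventilation status alone moves the odds ratio by at most about 0.04.

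**The case against.** The strongest reply is that the title and primary objective define independence relative to SpO2 and MAP. An association conditional on those two is estimable, and for a purely prognostic marker one need not condition on a treatment setting. This stands in part. A reader might infer that the plan cannot answer its question at all; the document does not support that. What the omission undermines is reading the result as gas exchange, or as independent of oxygen treatment. The plan does not say whether its aim is prognostic or aetiological, and it already adjusts beyond SpO2 and MAP (age, sex, ICU type, comorbidities and, in Section 5, ventilation), so a broader reading of independence is natural.

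Four further points are fair:
- The 6.6-fold figure is an upper bound at fixed PaCO2, from room air to pure oxygen. It is not the expected distortion; the document gives no FiO2 distribution.
- FiO2 need not itself cause death. In the simulation it matters because it tracks severity.
- Adding FiO2 as a linear term is not a complete cure. The FiO2-adjusted odds ratio still drifts with titration, from 0.70 / 0.58 to 0.90 / 0.85.
- The ventilation discrepancy between Sections 5 and 6.2 is a separate inconsistency, provable from the text alone. It needs correcting anyway and does not prove the FiO2 point.

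The existing safeguards do not answer the concern. Reporting by ventilation status is already planned, and the small shift when ventilation status is added suggests it is a weak substitute for FiO2.

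**Conclusion.** The point holds. FiO2 is an unaddressed determinant of the exposure, and the primary odds ratio as specified mixes gas exchange with oxygen treatment. Under the assumptions shown, leaving out FiO2 and ventilation status moved the odds ratio per SD from 0.58–0.90 to 0.69–1.08. It was attenuated in every scenario, masked in two at intermediate to strong titration, and reversed in three at the strongest settings.

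A reader might infer that the planned analysis will give the wrong sign. The document does not support that: reversal needs strong titration of FiO2 to severity, and in most scenarios the direction was preserved. The actual size depends on how oxygen was given in this cohort and cannot be derived from the document. The absence of FiO2 and the dropped ventilation covariate are plain from the text; the magnitude is illustrative only.

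**What to change.** 1. Add ventilation status to the 6.2 model so that it matches Section 5.
2. Add FiO2 at the time of the first blood gas to the covariates in Sections 5 and 6.2, modelled flexibly, for example with a spline.
3. Extend the missing-data rule in 6.4 to FiO2, and report how much is missing.
4. Report the model without FiO2 as a sensitivity analysis, so that readers can see how far the odds ratio moves.
5. If FiO2 is unavailable for most blood gases, do not describe the association as independent of oxygen treatment, and state this as a limitation. The ventilation subgroup should not be offered as a replacement.

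The cost is one more variable to extract from an existing database, with some missing values. The document does not say how completely FiO2 is recorded, and if it is mostly missing, imputation would be poorly supported and step 5 applies.
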